5.2 Handling of Study Interventions

Both interventions will be administered in doses of approximately 45 minutes (three 15-minute sessions) per week for 12 weeks without crossover at our facilities. Each intervention session will be supervised by Drs. [name] and/or [name].

5.3 Concomitant Interventions

5.3.1 Allowed Interventions

N/A

5.3.2 Required Interventions

N/A

5.3.3 Prohibited Interventions

Participants will not be allowed to participate in any other intervention or observational studies while enrolled in the intervention phase of this trial

5.4 Adherence Assessment

Sustaining adherence represents a major challenge in any RCT involving older adults. The phone-based delivery of the RCT improves likelihood of adherence. We have also incorporated multiple methods to promote adherence and reduce possibility of missing data.

- A permanent staff contact will be provided for each participant in the motor imagery and visual imagery intervention groups.
- Transportation and snacks will be provided on pre and post intervention assessment days.
- All participants will be compensated for attending in-house or telephone sessions (\$50 for the baseline visit, \$25 for the phone-based intervention, and \$50 for the post-intervention visit, for a total of \$125 for the study).

We propose to over-enroll by 20% to account for any attrition. Methods to account for non-compliance and missing data:

- Protocol violations. Subjects who miss 6 sessions due to any reason will be excluded from main analyses. We will explore dose response by adjusting number of sessions attended as a

covariate.

- We will identify 2 contact persons who do not live with the participant for when participant cannot be reached.
- Flexible scheduling with makeup sessions on alternate days.
- For each in-house study visit, we will allow a four-week window for completion.
- If the participant is acutely ill, is in the hospital, or has a temporary condition that interferes with walking (e.g. ankle sprain), we will attempt to complete the assessment at another time.
- Outcome adjudication. The research team will adjudicate events such as mobility disability in subjects who drop out based on medical interviews, contact interviews, and home assessments as required.

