6.2.4 Completion/Final Evaluation

Assessments to be completed at the final visit (12 months post-intervention) are listed in Table 5.1.

Losses to follow-up can be classified into non-informative (missing at random (MAR)) and informative censoring (drop out depends on the unobserved outcomes). No adjustment is necessary for non-informative censoring. However, for informative censoring, parameter estimates and resulting tests on hypotheses will be biased without further adjustment. The best way to handle missing data is to avoid it. However, we recognize that despite all our efforts there will be missing data.

Dropouts: We will follow-up with participants who dropped out of the study to determine both their mobility status and reasons for withdrawal. The research team will adjudicate events such as mobility disability in subjects who drop out based on medical interviews, contact interviews, and home assessments as required. Utilization of the telephone based

questionnaire to account for possible non-random drop-out will be administered. If the participant is acutely ill, is in the hospital, or has a temporary condition that interferes with walking (e.g. ankle sprain), we will attempt to complete the assessment at another time.

We also propose intention to treat (ITT) analysis, which includes all randomized participants in the groups assigned, regardless of their adherence with the entry criteria, whether motor imagery was received, and subsequent withdrawal or deviation from the protocol. ITT analysis is pragmatic because it admits noncompliance and protocol deviations, and gives an unbiased estimate of the intervention effect. Handling missing data is a major issue in ITT, and is dealt with by imputation or sensitivity analysis. Our statistician, [name], is very experienced in these methods.

A rich set of telephone-based information will be collected even for those subjects who may drop out. We will utilize this auxiliary information to assess the MAR assumption and combine it into the main model through joint modeling and multiple imputation approaches. [name] has applied these approaches to eliminate or reduce bias in presence of informative censoring in our other aging studies.

7 **SAFETY ASSESSMENTS**

7.1 **Specification of Safety Parameters**

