8 INTERVENTION DISCONTINUATION

Early study termination will occur in the event of any unanticipated serious adverse event determined to be possibly, probably or definitely related to study procedures, failure to recruit at least 50% of the projected number of subjects within 4 months, or failure to retain at least 75% of study subjects to the conclusion of the protocol.

Subjects may withdraw voluntarily from participation in the study at any time and for any reason. If the participant is acutely ill, is in the hospital, or has a temporary condition that interferes with walking (e.g. ankle sprain), we will attempt to complete the assessment at another time. We will follow-up with participants who dropped out of the study to determine both their mobility status and reasons for withdrawal. We will use intention to treat (ITT) analysis, which includes all randomized participants in the groups assigned, regardless of adherence with entry criteria, whether motor imagery was received, and subsequent withdrawal or deviation from the protocol. ITT analysis is pragmatic because it admits noncompliance and protocol deviations, and gives an unbiased estimate of the intervention effect. Handling missing data is a major issue in ITT, and is dealt with by imputation or sensitivity analysis. Our statistician, [name], is very experienced in these methods.

A rich set of telephone-based information will be collected even for those subjects who may drop out. We will utilize this auxiliary information to assess the MAR assumption and combine it into the main model through joint modeling and multiple imputation approaches.

The research team will adjudicate events such as mobility disability in subjects who drop out based on medical interviews, contact interviews, and home assessments as required. For each study assessment, we will allow a 4-week window for completion.

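### Section 5.4 drops participants who miss 6 sessions from the main analyses, Section 8 keeps everyone randomised, and Section 9.4 names no primary analysis set

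*Combined protocol and SAP*

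**What the plan says.** Section 5.4 lists missed sessions under protocol violations and rules: "Subjects who miss 6 sessions due to any reason will be excluded from main analyses".

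Section 8 takes the opposite line: "We will use intention to treat (ITT) analysis, which includes all randomized participants in the groups assigned, regardless of adherence with entry criteria", and also regardless of "whether motor imagery was received, and subsequent withdrawal or deviation from the protocol". It gives the reason: "ITT analysis is pragmatic because it admits noncompliance and protocol deviations, and gives an unbiased estimate of the intervention effect". Section 6.2.4 has nearly the same text but opens differently: "We also propose intention to treat (ITT) analysis, which includes all randomized participants in the groups assigned".

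For people who leave, Section 8 promises follow-up of mobility status and reasons for withdrawal. It adds: "A rich set of telephone-based information will be collected even for those subjects who may drop out". Mobility disability is to be adjudicated "based on medical interviews, contact interviews, and home assessments as required". The telephone data are to be used to assess the missing-at-random assumption, and the plan will "combine it into the main model through joint modeling and multiple imputation approaches".

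Section 9.4 gives the repeated-measures model for gait speed, its focus on the three-way interaction (time by trial type by imagery condition), the Bonferroni correction, and age, sex and education as covariates. It mentions no analysis set, neither intention to treat nor the 6-session exclusion.

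**The concern.** Two sections give different rules for who enters the main result, and the section that should decide between them is silent. Two analysts following the protocol could report different main results from the same data, and the choice could be made after both are known. The study is a pilot, but Section 9.1 gives its goal as determining efficacy, and Section 9.2 powers a test at alpha .05.

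If the exclusion governs, the groups compared are no longer the randomised groups, because attendance is observed after randomisation. The three-way test is then biased if two things hold together: exclusion differs by arm, and excluded people differ from retained people in their change in walking while talking (WWT) relative to their change in plain walking (W).

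**Working it through.** **1. The rules side by side**

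| Participant | Section 5.4 | Section 8 | Section 9.4 |
|---|---|---|---|
| Misses 6 sessions, attends post visit | out | in | silent |
| Drops out with 6 or more sessions left | out | in, with telephone data feeding the main model | silent |
| Misses fewer than 6, attends post visit | in | in | silent |

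The second row matters most. Anyone who drops out with 6 or more sessions left has missed 6, so Section 5.4 removes from the main analyses people whose data Section 8 brings into the main model.

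For dropouts the plan does not explicitly promise gait speed on the walkway. An all-randomised analysis therefore relies on the multiple imputation already named in Sections 6.2.4 and 8.

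**2. How many people could be affected**

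There are 36 sessions (Section 5.1). The documents give no miss rate. It cannot be inferred either, because Section 5.1 skips a session when the participant cannot be reached, while Section 5.4 offers makeup sessions. Assuming independent misses at rate p, the number missed is X ~ Binomial(36, p):

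| Assumed p | P(X ≥ 6) |
|---|---|
| 5% | 0.8% |
| 10% | 14.5% |
| 15% | 45.9% |

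The two sets could be nearly identical or very different.

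**3. Bias if the exclusion governs**

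The three-way term compares the arms on (WWT change minus W change). Let p1 and p0 be the proportions excluded in the two arms. Let dWWT and dW be the amounts, in SD of change, by which excluded people fall below retained people. With equal randomised groups, restricting to retained people raises an arm's mean contrast by its p times (dWWT − dW). So

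bias = (p1 − p0) × (dWWT − dW).

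It is zero if p1 = p0 or if dWWT = dW. For illustration, with inputs that are not in the documents, take p1 = 25%, p0 = 10% and dW = 0:

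- dWWT = 0.5: 0.15 × 0.5 = 0.075 SD
- dWWT = 1.0: 0.15 × 1.0 = 0.15 SD

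Type I error was simulated with 24 per arm before exclusion, no treatment effect, a nominal two-sided 5% test and 200,000 runs (Monte Carlo SE about 0.05 percentage points):

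| Case | Correlation of W and WWT change 0.3 | 0.5 | 0.7 |
|---|---|---|---|
| dWWT = 0.5 | 5.4% | 5.6% | 6.0% |
| dWWT = 1.0 | 6.7% | 7.4% | 9.1% |

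The zero-bias cases gave 4.96% to 5.06%.

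**4. Power under each rule**

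First, the plan's own figure. Section 9.2 gives n = 34 for f = .25, alpha .05 and power .80. I used a noncentral F with λ = N·f²·2/(1 − ρ) and 1 and N − 2 degrees of freedom. The two measurements and ρ are assumptions. At ρ = 0.5, λ = 34 × 0.0625 × 4 = 8.5 and power is 0.807, which reproduces 34.

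Next, suppose a share of 48 analysed participants gain nothing, so that f shrinks in proportion. Compare this with excluding 25%:

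| Case | N | f | ρ = 0.3 | ρ = 0.5 | ρ = 0.7 |
|---|---|---|---|---|---|
| No dilution | 48 | .25 | 0.82 | 0.92 | 0.99 |
| All kept, 18% gain nothing | 48 | .25 × 0.82 = .205 | 0.65 | 0.79 | 0.95 |
| All kept, 25% gain nothing | 48 | .25 × 0.75 = .1875 | 0.58 | 0.72 | 0.91 |
| All kept, 25% keep half the effect | 48 | .25 × 0.875 = .21875 | 0.71 | 0.84 | 0.97 |
| 25% excluded | 36 | .25 | 0.69 | 0.83 | 0.96 |

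Break-even at 25%, ignoring the change in degrees of freedom: 48·f_d² = 36·f², so f_d = 0.866f. If the less adherent keep a fraction g of the effect, 1 − 0.25(1 − g) = 0.866 and g = 0.46. At 18% the same steps give g = 0.475.

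**The case against.** The best defence is that the plan does rank the rules. Section 5.4 calls its set the main one, and Section 6.2.4 introduces intention to treat with the word *also*. Read together, they describe a per-protocol main analysis with intention to treat as an addition. That would be open to criticism but not contradictory. The reading does not hold up: Section 8 states intention to treat without *also* and puts dropouts' data into the main model. Even if it did hold, the main estimate would be conditioned on attendance and would lose the property for which Section 8 recommends intention to treat.

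A second objection is that the bias is hypothetical. This stands as to size. Calls have the same length, number and schedule in both arms, so the documents give no specific reason to expect attendance to differ. Misses probably cluster through illness or travel, so the binomial range is only a guide. Inflation is modest unless the deficit is large and confined to WWT. The point therefore rests on the undefined primary set, not on these figures.

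Third, the power figures are for 48 analysed participants and a two-measurement interaction. Section 9.2 enrols 58 to complete 48, and imputation for those without a post visit is not costed. This is a fair limit: the figures show the trade-off and do not give the power of the proposed analysis.

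**Conclusion.** The concern holds and must be fixed. That Sections 5.4 and 8 give incompatible main sets, and that Section 9.4 does not choose, follows from the text and needs no assumption. Its numerical effect is unknown. The share affected runs from 0.8% to 45.9% over assumed independent miss rates of 5% to 15%. The bias is zero when exclusion is equal by arm or affects W and WWT change equally; in the illustrative cases it is 0.075 to 0.15 SD, with type I error of 5.4% to 9.1%. Those cases rest on assumed exclusion rates, deficits and correlations.

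**What to change.** Amend four places so that they agree:

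- **Section 9.4:** *The primary analysis set is all randomised participants, analysed as assigned. Missing post-visit gait speed is handled by the multiple imputation named in Sections 6.2.4 and 8.*
- **Section 5.4:** replace the exclusion with *Participants who miss 6 or more sessions, for any reason, are excluded only from a per-protocol sensitivity analysis.* The present wording leaves open whether it means exactly 6 or at least 6. It also leaves open whether a session made up later counts as missed; reconcile this with the skipped-session text in Section 5.1.
- **Section 6.2.4:** delete the word *also*.
- **Section 8:** state that intention to treat is the primary analysis.

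The cost is a text amendment reported to the IRB under Section 10.3.4, with no new visit or procedure. The statistical downside is possible dilution. At assumed ρ = 0.5, power falls from 0.92 to 0.79 or 0.72 if 18% or 25% of 48 analysed participants gain nothing. That is an extreme case, since someone who misses exactly 6 sessions has still received 30, and the plan's own 18% is attrition, a different quantity. Exclusion has its own cost: removing 25% leaves 36 participants and power of 0.83. If the less adherent keep about 46% or more of the effect, the all-randomised analysis has at least as much power as the exclusion.

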9.2 Sample Size and Randomization

The primary hypothesis examines change in gait speed (during NPW and WWT conditions). Setting an alpha level of .05, power of .80 and a medium effect size of defined as $f=.25$, the necessary sample size for detecting an interaction between time of test (pre and post), trial type (W or WWT) and imagery condition (Imagined gait or AC) is $n = 34$. Thus, our study completion goal of $n = 48$ (58 enrolled; 48 completed) is sufficient to detect our effects of interest and account for the 18% attrition rate expected during the study period (as observed in our previous studies (64)).

To detect a BOLD signal change at the individual subject level (i.e. first-level time-series modeling using SPM) at $p < 0.001$, a percent signal change of 0.34% is required using a published method and estimate of noise at a magnet strength of 3.0 Tesla (65). Based on this estimate, to detect a difference in contrast values between groups (i.e. second level analyses using SPM) at $p < 0.001$ and a power of at least .80, where the mean of one group's signal change is 50% of the other, 16 subjects per group are required. Thus, our study completion goal of $n = 48$ (24 in each condition) is sufficient to detect a main effect of imagery condition (imagined gait vs. AC) and leave room for the detection of interactions

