9.4 Data Analyses

9.4.1 Primary outcome.

To examine gait speed during W and WWT we will use repeated-measures analyses that include time of test (pre and post), and trial type (W or WWT) as within subjects factors, and imagery condition (imagined gait or AC) as the between-subjects factor. Consideration of these analyses will focus on the three-way interaction between time of test, trial type, and imagery condition.

9.4.2 Secondary and tertiary outcomes.

Similar repeated-measures analyses will be used for our secondary outcomes measures/additional EF measures: Trail Making Test, the Letter Number Sequencing Test, the Stroop Color and Word Test, and the Flanker Interference Task. These measures include the time to complete Trails B corrected for Trails A from the Trail Making Test (Trails B-A), the raw score from the letter-number sequencing task WAIS-III, the raw response time to Color-Word (incongruent) trials corrected for Color (congruent) trials from the Stroop Color and Word Test (i.e., Stroop Interference) and the flanker interference response time measure (incongruent-congruent trials) from the Flankers interference task. Although three of these four measures are difference scores, our analyses will be completed on raw scores in order to maximize power. More specifically, for these measures we will use repeated-measures analyses that included time of test (pre and post) and trial type as within subjects factors, and imagery condition (imagined gait or AC) as the between-subjects factor. Trial type for the Trail Making Test will be Trails A and Trails B. Trial Type for the Stroop Color and Word Test will be congruent trials and incongruent trials. Finally, trial type for the Flanker task will be congruous and incongruous trials. Consideration of these analyses will focus on the three-way interaction between time of test, trial type, and condition. Analyses will focus on the primary outcome variables during training and to the end of training period.

All behavioral analyses will be corrected for multiple comparisons using the Bonferroni correction.

We will use a whole-brain multivariate Ordinal Trend Covariance Analysis (OrT-CVA) to analyze the BOLD signal during imagined walking and walking while talking (66, 67). This is because we are interested in determining how the use of the entire locomotion and executive

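### Section 5.4 drops participants who miss 6 sessions from the main analyses, section 8 commits to ITT, and section 9.4 does not say which analysis set is primary

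*Combined protocol and SAP*

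**What the plan says.** Four places in the combined protocol and SAP bear on who is analysed.

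- **Section 5.4**, among the methods for non-compliance and missing data and labelled as a protocol violation: "Subjects who miss 6 sessions due to any reason will be excluded from main analyses". The next sentence plans an exploratory dose-response analysis with the number of sessions attended as a covariate. The same list allows make-up sessions.
- **Section 6.2.4**: "We also propose intention to treat (ITT) analysis, which includes all randomized participants in the groups assigned".
- **Section 8** has nearly the same paragraph without the word 'also': "We will use intention to treat (ITT) analysis, which includes all randomized participants in the groups assigned". It applies this regardless of whether motor imagery was received, and despite later withdrawal or deviation. It calls ITT the unbiased approach and plans to use telephone-based information and "combine it into the main model through joint modeling and multiple imputation approaches".
- **Section 9.4.1** gives the primary model (time, trial type and imagery condition, with the focus on their three-way interaction). Neither it nor the rest of section 9 mentions ITT, a per-protocol set or the 6-session rule.

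**The concern.** A participant who misses 6 of the 36 sessions is out of the main analyses under 5.4 and in the analysis under section 8. Nothing in the plan says which rule governs the primary gait-speed result.

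The choice matters because attendance is observed after randomisation and may be related both to the outcome and to the arm. The two arms do different tasks, so the people who keep attending need not be alike. Comparing adherers with adherers answers a different question from comparing everyone as randomised, and section 8 gives the reason for preferring the latter. With both rules in the text, an analyst could run the model on each set and report either as the main result, each time citing the protocol. The trial is a pilot, but it has a stated efficacy aim and a powered hypothesis test, and it is meant to inform a full-scale RCT.

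**Working it through.** **1. The texts side by side.** Take one randomised participant who missed 6 sessions and attended the post-intervention visit.

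| Section | Is this participant in? | Which analysis? |
|---|---|---|
| 5.4 | No | Main analyses |
| 6.2.4 | Yes | ITT, also proposed |
| 8 | Yes | ITT, to be used |
| 9.4.1 | Not stated | Primary model |

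Sections 9.1 to 9.3 do not rank the sets either. The count of missed sessions is also loose. The rule does not say 6 or more, section 5.1 says a call that cannot be completed that day is skipped, and 5.4 allows make-ups.

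**2. The plan's sample size.** Section 9.2 gives n = 34 for alpha 0.05, power 0.80 and f = 0.25. I used the noncentral F for a within-between interaction with 2 groups and m = 2 measurements, lambda = f² × N × m / (1 − ρ), on 1 and N − 2 degrees of freedom. The plan states no correlation, so ρ = 0.5 is my assumption. At N = 34, lambda = 0.0625 × 34 × 2 / 0.5 = 8.5 and power is 0.807, which reproduces the plan's 34. At the 48 completers planned, power is 0.924.

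**3. How many the rule could remove (illustration only).** The documents give 36 sessions and no miss rate. Reading the rule as 6 or more missed, with independent misses at rate p and no make-ups, the share excluded is q = 1 − P(X ≤ 5), X ~ Binomial(36, p).

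| p (assumed) | q, independent misses | q, within-person correlation 0.1 (assumed, beta-binomial) |
|---|---|---|
| 5% | 0.8% | 9.7% |
| 10% | 14.5% | 24.0% |
| 15% | 45.9% | 40.4% |

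Make-ups push the other way. If half of missed sessions were made up (assumption), a 10% rate becomes 5% and q falls from 14.5% to 0.8%; a 15% rate becomes 7.5% and q falls from 45.9% to 5.0%. The range is too wide to support any single figure.

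**4. When the number would fall below 34.** Of 48 completers, 48 − 34 = 14 can be lost, and 14/48 = 29.2%. Under the independent model that share is reached at p of about 12.5%.

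**The case against.** The strongest reply is that the texts can be reconciled. Section 5.4 defines the main analyses, 6.2.4 adds ITT, and section 8 largely repeats 6.2.4. No sentence calls ITT the primary or only analysis, and the mention of a main model in section 8 concerns auxiliary data and does not define a population. On this reading both analyses would be reported. This stands in part: the fair description is an unstated ranking, and a reader who infers that the plan names two different primary sets goes beyond the text. It does not settle the matter, because section 8 commits to ITT without qualification. If ITT were only supplementary, the headline result would still rest on adherers.

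Four stronger readings are tempting, and the documents do not support them.

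- **A definite bias.** Nothing in the plan gives an adherer-to-non-adherer difference. The primary contrast is the three-way interaction, so a difference in change that is equal for walking and walking while talking would cancel. Bias is possible, but its size and direction are unknown.
- **A threat to power.** More than 29% of 48 completers would have to go before the plan's 34 is missed.
- **Losses on top of the 18% attrition.** Section 9.2 does not define a completer, so heavy missers may already be among those counted as lost.
- **No useful data on dropouts.** Section 8 follows them "to determine both their mobility status and reasons for withdrawal", but it also plans interviews, home assessments as required and telephone-based information. Nor does any section withhold the post-intervention visit from people who miss sessions.

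**Conclusion.** The point holds. Section 5.4 and section 8 give different answers for the same participant, 6.2.4 does not resolve them, and 9.4 is silent, so the primary analysis set is not fixed in advance. This rests on the text alone and needs no assumption about attendance.

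The practical size is unknown. The illustrative exclusion shares of 0.8%, 14.5% and 45.9% depend on assumed miss rates of 5%, 10% and 15%, independent misses and no make-ups. Even the reassuring 5% case becomes 9.7% under modest clustering, so it should not be called negligible. The main issue is which effect is estimated and the freedom to choose the set later; loss of power is secondary. It is a minor, easily corrected gap, best closed before anyone sees outcome data by arm.

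**What to change.** - **Section 9.4.1:** state that the primary gait-speed analysis is ITT with all randomised participants in their assigned arm. Use observed post-intervention data whatever the number of sessions attended, and the multiple imputation already planned in 6.2.4 and 8 where the outcome is missing.
- **Section 5.4:** let missing 6 or more of 36 sessions define only a per-protocol sensitivity analysis, and say whether a made-up session counts as missed. The exploratory dose-response analysis can stay.
- **Section 6.2.4:** align its wording with section 8.

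The cost is a few sentences, with no new visit. There are two downsides. Low attenders may dilute the effect. With the formula above, N = 48, ρ = 0.5 and no effect at all in them, f becomes 0.25 × (1 − q), and power is 0.863, 0.774 or 0.661 when they make up 10%, 20% or 30% of the sample. Excluding them would give about 0.900, 0.851 or 0.807 (N = 44, 38 or 34 after rounding to even numbers). This is pessimistic, since someone who misses 6 sessions has had 30 of 36, or 83%. Second, imputation for true dropouts may be weak, because gait speed is not collected by phone, although the other follow-up in section 8 helps.
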